10.7 Protocol Amendments

Changes to the protocol may be made only by the Sponsor (with or without consultation with the Investigator). All protocol modifications must be submitted to the site IRB/EC in accordance with local requirements and, if required, to regulatory authorities, as either an amendment or a notification. Approval for amendments must be awaited before any changes can be implemented, except for changes necessary to eliminate an immediate hazard to trial subjects, or when the changes involve only logistical or administrative aspects of the trial. No approval is required for notifications.

11 STUDY MONITORING, AUDITING, AND INSPECTING

11.1 Quality Control and Quality Assurance

The Sponsor or designees and regulatory authority inspectors are responsible for contacting and visiting the Investigator for the purpose of inspecting the facilities and, upon request, inspecting the various records of the trial (e.g., eCRFs and other pertinent data) provided that subject confidentiality is respected.

The Sponsor's or designee's monitor is responsible for inspecting the eCRFs at regular intervals throughout the study to verify adherence to the protocol; completeness, accuracy, and consistency of the data; and adherence to local regulations on the conduct of clinical research. The monitor should have access to subject medical records and other study-related records needed to verify the entries on the eCRFs.

The Investigator agrees to cooperate with the monitor to ensure that any problems detected in the course of these monitoring visits are resolved.

In accordance with ICH guidance on GCP and the Sponsor's audit plans, a certain percentage of sites participating in this study will be audited. These audits may include a review of site facilities (e.g., pharmacy, drug storage areas, and laboratories) and review of study-related records may occur in order to evaluate the trial conduct and compliance with the protocol, ICH guidance on GCP, and applicable regulatory requirements.

The Sponsor's or designee's representatives, regulatory authority inspectors and IRB/EC representatives who obtain direct access to source documents should also respect subject confidentiality, taking all reasonable precautions in accordance with applicable regulatory requirements to maintain the confidentiality of subjects' identities.

11.2 Risk Management

ACADIA utilizes the ICH E6 (GCP) Revision 2 risk management approach that includes methods to assure and control the quality of the trial proportionate to the risks inherent in the trial and the importance of the information collected. The intent is that all aspects of this trial are operationally feasible and that any unnecessary complexity, procedures, and data collection are avoided. The ACADIA risk management approach includes the following activities with a focus on critical processes and critical study data:

- Risk Identification: risks to critical trial processes, governing systems, investigational product, trial design, data collection, and recording are identified.
- Risk Evaluation: identified risks are evaluated by considering the following factors:
(a) likelihood of occurrence, (b) impact on human subject protection and data integrity, and (c) detectability of errors.
- Risk Control: risks that can be reduced (e.g., mitigating) or can be accepted are differentiated. Risk mitigation activities are incorporated in protocol design and implementation, study plans, training, processes, and other documents governing the oversight and execution of study activities. Where possible, predefined quality tolerance limits are to be defined to identify systematic issues that can impact subject safety or data integrity and deviations from the predefined quality tolerance limits will

trigger an evaluation and possibly an action. Contingency plans are developed for issues with a high risk factor that cannot be avoided.

- Periodic risk review, communication, and escalation of risk management activities are ongoing during trial execution and risk outcomes are reported in the clinical study report (CSR).

12 ETHICAL CONSIDERATIONS

12.1 Ethical Standard

The study will be conducted in compliance with the protocol, the Declaration of Helsinki, ICH GCP, and other applicable regulatory requirements (e.g., Serious Breach reporting, urgent safety measures, and EU GDPR).

The study will be performed in accordance with the US Health Insurance Portability and Accountability Act (HIPAA) regulations, US FDA GCP Regulations (US Code of Federal Regulations [CFR] 21 parts 50, 54, 56, and 312), and ICH guidance on GCP (E6) and clinical safety data management (E2A).

In accordance with Directive 75/318/EEC, as amended by Directive 91/507/EEC, the final clinical study report will be signed by an Investigator and/or Coordinating Investigator who will be designated prior to the writing of the clinical study report.

12.2 Institutional Review Board/Ethics Committee

The Investigator or designee will provide the IRB/EC with all requisite material, including a copy of the protocol, informed consent, and any subject information or advertising materials. The study will not be initiated until the IRB/EC provides written approval of the protocol and the informed consent and until approved documents have been obtained by the Investigator and copies received by the Sponsor. All amendments will be sent to the IRB/EC for information (minor amendment) or for submission (major amendment) before implementation. The Investigator will supply the IRB/EC and the Sponsor with appropriate reports on the progress of this study, including any necessary safety updates, in accordance with the applicable government regulations and in agreement with policy established by the Sponsor.

12.3 Informed Consent Process

In accord with the provisions of the US CFR 21 part 50, and since this study involves greater than minimal risk but presents the prospect of direct benefit to all subjects enrolled, consent shall be obtained from an LAR, typically a guardian, or at least one parent, in accordance with local IRB requirements. Minors will be given the opportunity to assent to participation if and when they are considered capable of doing so by the PI and per local IRB requirements.

Properly executed, informed consent/assent must be obtained from each LAR/subject prior to the final procedures being performed at the EOT visit in the antecedent study. Subjects who enter the present study under special circumstances due to the COVID-19 public health emergency will have consent obtained for the present study before any procedures are performed (e.g., such as the blood draw before the Baseline visit). The LAR is defined as “An individual or judicial or other body authorized under applicable law to consent on behalf of a prospective subject to the subject’s participation in the procedures involved in the research” (US CFR 21 part 50).

For subjects who are minors, written informed consent will be obtained from the LAR. For subjects who are not minors, written informed consent will be obtained from the LAR or the subject if deemed able by the Investigator. When consent is being provided by an LAR, subject assent for participation should be documented, when possible. Assent is the affirmative agreement to participate in the research of a minor or of an adult who does not have the capacity to consent. If written assent is not possible, verbal assent is allowed and must be documented. If subject assent is not possible, then the site must document rationale for not being able to provide written or documented subject assent.

If a subject’s 18th birthday takes place during the study and the subject is deemed able to consent by the Investigator, the subject should sign the informed consent. Reconsenting should take place if required by and in accordance with IRB or EC policy and applicable local law.

The subject’s caregiver must also provide informed consent regarding their participation in the study prior to participating in any study procedures.

The informed consent must, at a minimum, include the elements of consent described in the ICH guidance on GCP and the US CFR 21 part 50.25. A copy of the ICF planned for use will be reviewed by the Sponsor or designee for acceptability and must be submitted by the Investigator or designee together with the protocol, to the appropriate IRB/EC for review and approval prior to the start of the study at that investigational site. Consent forms must be in a language fully comprehensible to the LAR of the prospective subject. The Investigator must provide the Sponsor or designee with a copy of the IRB/EC letter approving the protocol and the ICF before the study drug supplies will be shipped and the study can be initiated.

The consent form must be revised if new information becomes available during the study that may be relevant to the subject. Any revision must be submitted to the appropriate IRB/EC for review and approval in advance of use.

12.3.1 Consent and Other Informational Documents Provided to Subjects

The subject/LAR must be given a copy of the signed informed consent and the original maintained in the designated location at the site.

12.3.2 Consent Procedures and Documentation

It is the Investigator or designee's responsibility to obtain written informed consent from the subject/LAR after adequate explanation of the aims, methods, anticipated benefits, and potential hazards of the study. The LAR must be given ample time to decide about study participation and opportunity to inquire about details of the study. The IRB/EC-approved consent form must be personally signed and dated by the LAR with subject assent, if possible, and by the person who conducted the informed-consent discussion. The Investigator or appropriate site personnel must document the details of obtaining informed consent in the subject's study documents.

The subject's caregiver must also indicate their understanding of the study and their role as a caregiver to the subject during the study. The subject's caregiver must provide written consent prior to any study procedures being performed indicating their agreement to participate in the study in the caregiver role.

Participation in the testing for identification of biomarkers is optional. Informed consent must be obtained, as appropriate, prior to blood draws for this procedure.

Records related to a study subject's participation will be maintained and processed according to local laws, and where applicable, the European Union General Data Protection Regulation (EU GDPR). The consent and study information documentation will include statements describing local and regional requirements concerning data privacy, and who to contact for questions.

13 PUBLICATION PLAN

All publication rights are delineated in the Clinical Study Agreement and/or other separate agreements with the Investigator and/or Institution, as applicable.

14 CONFLICT OF INTEREST POLICY

14.1 Finance, Insurance, and Indemnity

Arrangements for finance, insurance, and indemnity are delineated in the Clinical Study Agreement and/or other separate agreements with the Investigator and/or Institution, as applicable.

| 20. | REFERENCES | 50 |
| 21. | APPENDICES | 51 |
| 21.1 | Schedule of Assessments..... | 51 |
| 21.2 | Summary of Version Changes..... | 53 |

LIST OF TABLES

| | | |
|---------|--|----|
| Table 1 | Dosing Schedule Based on Weight at Baseline of the Present Study | 15 |
| Table 2 | Analysis Visit Windows..... | 23 |
| Table 3 | Dosing Schedule and Total Expected Volume Based on Weight at Baseline of the Present Study..... | 30 |
| Table 4 | Conversion of Height of Remaining Liquid (cm) into Volume (mL)..... | 31 |
| Table 5 | Criteria for Potentially Clinically Important Laboratory Values – Hematology and Chemistry | 40 |
| Table 6 | Criteria for Potentially Clinically Important Laboratory Values - Urinalysis | 41 |
| Table 7 | Criteria for Potentially Clinically Important Vital Signs..... | 42 |
| Table 8 | Criteria for Potentially Clinically Important ECG Values..... | 43 |

LIST OF FIGURES

| | | |
|----------|--------------------------------|----|
| Figure 1 | Schematic of Study Design..... | 14 |
|----------|--------------------------------|----|

ABBREVIATIONS

| | |
|----------|---|
| AE | adverse event |
| ATC | Anatomical/Therapeutic/Chemical |
| BMI | body mass index |
| CGI-I | Clinical Global Impression – Improvement |
| CGI-S | Clinical Global Impression – Severity |
| COVID-19 | coronavirus disease 2019 |
| DSMB | Data and Safety Monitoring Board |
| eCRF | electronic case report form |
| ECG | Electrocardiogram |
| EDC | electronic data capture |
| FDA | Food and Drug Administration |
| GJ | Gastrojejunal |
| GSD | Guidance for Site Documentation and Data Management Querying of Data Impacted by COVID-19 |
| ICND | Impact of Childhood Neurologic Disability Scale |
| MedDRA | Medical Dictionary for Regulatory Activities |
| NDA | new drug application |
| PCI | potentially clinically important |
| PD | pharmacodynamic(s) |
| PHE | public health emergency |
| PK | pharmacokinetic(s) |
| QTcB | QT Interval Corrected for Heart Rate using Bazett's Formula |
| QTcF | QT Interval Corrected for Heart Rate using Fridericia's Formula |
| RSBQ | Rett Syndrome Behaviour Questionnaire |
| RTT | Rett Syndrome |
| RTT-AMB | Rett Syndrome Clinician Rating of Ambulation and Gross Motor Skills |
| RTT-CBI | Rett Syndrome Caregiver Burden Inventory |
| RTT-COMC | Rett Syndrome Clinician Rating of Ability to Communicate Choices |
| RTT-CSS | Rett Syndrome Clinical Severity Scale |

| | |
|----------|--|
| RTT-HF | Rett Syndrome Clinician Rating of Hand Function |
| RTT-VCOM | Rett Syndrome Clinician Rating of Verbal Communication |
| SAE | serious adverse event |
| SAP | statistical analysis plan |
| SD | standard deviation |
| SE | standard error |
| SOC | system organ class |
| TEAE | treatment-emergent adverse event |

1. INTRODUCTION

This statistical analysis plan (SAP) provides a technical and detailed elaboration of the statistical analyses of efficacy and safety data as described in the protocol amendment 2, dated 07 August 2020.

Specifications for tables, figures, and listings are contained in a separate document. Statistical analyses for population pharmacokinetic (PK) and PK/pharmacodynamics (PD) modeling will be presented in a separate report and therefore will not be included in this SAP.

This plan should be read in conjunction with the study protocol and the electronic case report forms (eCRFs).

2. OBJECTIVES

2.1 Primary Objective

The primary objective of this study is to investigate the safety and tolerability of long-term treatment with oral trofinetide in girls and women with Rett syndrome.

2.2 Secondary Objectives

The secondary objectives for this study are:

- To investigate the efficacy of long-term treatment with oral trofinetide in girls and women with Rett syndrome
- To investigate the efficacy of long-term treatment with oral trofinetide in girls and women with Rett syndrome on overall ability to communicate
- To investigate the benefit of long-term treatment with oral trofinetide on overall quality of life for girls and women with Rett syndrome
- To investigate the efficacy of long-term treatment with oral trofinetide in girls and women with Rett syndrome on:
 - Hand function
 - Ambulation and other gross motor skills
 - Ability to communicate choices and preferences
 - Ability to communicate verbally
- To investigate the efficacy of long-term treatment with oral trofinetide on a global assessment of the severity of illness in girls and women with Rett syndrome
- To investigate the benefit of long-term treatment with oral trofinetide on the burden on caregivers of girls and women with Rett syndrome
- To investigate the benefit of long-term treatment with oral trofinetide on the impact of the disability on the child's and family's everyday life

2.3 Pharmacokinetic Objectives

The pharmacokinetic objectives of this study are:

- To characterize the pharmacokinetics (PK) of trofinetide in girls and women with Rett syndrome following long-term treatment with oral trofinetide

- To assess the pharmacokinetic/pharmacodynamic (PK/PD) relationship using safety and efficacy endpoints in girls and women with Rett syndrome following long-term treatment with oral trofinetide

3. STUDY DESIGN

3.1 General Study Design

This is a 40-week, multicenter, open-label extension (OLE) study to evaluate long-term safety and tolerability of trofinetide in girls and women with Rett syndrome. Subjects who complete the preceding double-blind study (ACP-2566-003) will be eligible to enroll in the OLE.

The Week 12/EOT visit of the antecedent study will serve as the Baseline visit of the present study. The data gathered at the Week 12/EOT visit of the antecedent study serves as the baseline data of the present study.

Because of the special circumstances surrounding the Coronavirus Disease 2019 (COVID-19) public health emergency in the spring of 2020, subjects who were discontinued from Study ACP-2566-003 before completion because of the COVID-19 public health emergency and subjects who completed Study ACP-2566-003, but were prevented from entering the present study because of the COVID-19 public health emergency, may be re-evaluated for eligibility at the Baseline visit of the present study.

However, subjects who are discontinued from Study ACP-2566-003 for other reasons other than COVID-19 pandemic, or who are not able to rollover to this study at the Week 12/EOT visit of the antecedent study, will not be able to enter the present study.

[figure not shown]
The duration of participation for individual study subjects will be approximately 44 weeks. Approximately 28 sites will participate in this study.

The study will have two periods ([Figure 1](#)):

- Treatment period: 40 weeks
- Safety follow-up period: 30 days

The study design is summarized in Figure 1.

Figure 1 Schematic of Study Design

^a Subjects who roll over into the subsequent open-label study (ACP-2566-005) will not have the safety follow-up telephone call or telemedicine visit.

The schedule of events and assessments is provided in the appendix ([Section 21.1](#)). As shown in the schedule of events, study visits may be done off-site rather than in the clinic with the prior approval of the Sponsor or Medical Monitor.

For subjects who remained on the originally assigned dose in the antecedent study, the assigned dose in this study will be based on the subject's weight at the Baseline visit of the present study, as outlined below in [Table 1](#). Thus, for a particular subject whose weight at the Baseline of this study moves them into a different weight category according to Table 1, the assigned dose given in this study may be different from the originally assigned dose given in the antecedent study. After Baseline the dose will not be changed based on a change in weight that places the subject into a different weight category.

Subjects whose originally assigned dose in the antecedent study was decreased for tolerability reasons will remain on that same dose in this study. The dose should be increased at some point during the study, if tolerated, to the dose that would have been assigned based on the weight category at Baseline of the present study.

Table 1 Dosing Schedule Based on Weight at Baseline of the Present Study

| Weight | Dose | Total Daily Dose |
|-----------|------------------|------------------|
| 12-20 kg | 30 mL (6 g) BID | 60 mL (12 g) |
| >20-35 kg | 40 mL (8 g) BID | 80 mL (16 g) |
| >35-50 kg | 50 mL (10 g) BID | 100 mL (20 g) |
| >50 kg | 60 mL (12 g) BID | 120 mL (24 g) |

Abbreviations: BID=twice daily

3.2 Schedule of Assessments

The schedule of assessments is in the Appendix ([Section 21.1](#)).

3.3 Randomization

Not Applicable. This is not a randomized study.

3.4 Blinding

This is an open-label extension study in which all patients will receive trofinetide. However, the investigators will not be unblinded of the antecedent study's, ACP-2566-003, treatment assignment during the conduct of study ACP-2566-004.

3.5 Determination of Sample Size

Up to approximately 180 subjects will be enrolled. The sample size for this study is not based on statistical considerations, but will depend on the number of subjects who transition into this open-label extension study from the antecedent study.

3.6 Coronavirus Disease 2019

In March 2020, the emerging coronavirus disease 2019 (COVID-19) pandemic resulted in implementation of urgent safety measures designed to ensure subject safety. Mechanisms to record information on the potential impact of the COVID-19 pandemic on data itself, as well as data collection and integrity, were implemented (as detailed in the appendix of ACP-2566-004's Data Management Plan titled "Guidance for Site Documentation and Data Management Querying of Data Impacted by COVID-19" [GSD] included in eTMF).

Relationship to the public health emergency caused by the COVID-19 pandemic will be assessed for early terminations, protocol deviations, selected medications, and selected adverse events as detailed in the GSD.

4. ANALYSIS SETS

Safety Analysis Set

The Safety Analysis Set consists of all subjects who received at least one dose of study drug in this study.

Pharmacokinetics (PK) Analysis Set

The PK Analysis Set consists of the subjects in Safety Analysis Set with at least one measurable trofinetide whole blood concentration. Subjects will be classified according to the actual treatment received.

5. DATA HANDLING CONVENTIONS

All data collected in the study will be listed.

5.1 General Data Reporting Conventions

Continuous variables will be summarized using the following descriptive statistics: number of subjects, mean, standard error (SE), standard deviation (SD), median, minimum, and maximum. For descriptive summaries of efficacy, the 95% confidence interval (CI), calculated as $\text{mean} \pm 1.96 * \text{SE}$, will be presented. Unless specified otherwise, means, medians, and CIs will be presented to one more decimal place than the raw data, and the SDs and SEs will be presented to two more decimal places than the raw data. In general, the maximum number of decimal places is 4 and values will be truncated to 4 decimal places in situations where there are more than 4 decimal places. Wherever possible data will be decimal aligned.

Height, weight and BMI will be presented with a maximum of one decimal place.

Categorical variables will be summarized by the number of subjects and the percentage of subjects in each category; the number of subjects and the percentage of subjects with missing data will be summarized for demographic and baseline characteristics (if applicable). Categories with zero counts will not have zero percentages displayed. For demographic summaries, percentages will be calculated by using the total number of subjects in the given treatment group of the antecedent study as the denominator. Percentages will be presented with one decimal place.

Duration in months will be calculated as ([the number of days / 365.25] *12).

Lab values, not including PK concentration data, that are collected with “<” or “>” signs will generally be analyzed as the numerical value without the sign in tables and figures. In listings, these data will be reported as collected with the sign.

For each continuous measure in safety and efficacy analyses, change from baseline results will be presented by treatment group of the antecedent study and overall in two ways:

1. Main analysis: using the baseline of this study, as defined in [Section 5.5](#), to report the changes across the timepoints of this open-label Study ACP-2566-004.
2. Exploratory analysis: using the baseline from the antecedent study, ACP-2566-003, to report the changes across the timepoints of this open-label Study ACP-2566-004.

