9. MEDICAL HISTORY

Medical history reported terms will be coded with Medical Dictionary for Regulatory Activities (MedDRA), version 23.0 or newer. The subject incidence will be summarized for each system organ class (SOC) and preferred term for the Safety Analysis Set. A subject will be counted only once per SOC or per preferred term for the summary.

A listing of the SOC, preferred term, body system, verbatim for the medical history condition/event, start and stop dates (when available), and an indicator for whether or not the condition is ongoing will be provided.

Rett Syndrome History

The age at Rett syndrome diagnosis, the age at first symptoms noticed, the number and percentage of subjects by *MECP2* gene mutation, and the number and percentage of subjects with more than one *MECP2* mutation (Yes, No) collected on the Rett History eCRF page will be summarized.

Rett syndrome history will be listed.

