12. EFFICACY ANALYSES

Unless otherwise specified, all efficacy analyses will be performed using the Safety Analysis Set. No hypothesis testing is planned. Descriptive summaries of all efficacy endpoints will be presented.

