12.5 Examination of Subgroups

Subgroup analysis by *MECP2* mutation groupings may be performed for RSBQ and CGI-I.

12.5.1 *MECP2* Mutation Groupings

The number and percentage of subjects will be examined in the following *MECP2* mutation groupings.

| Mutations | Code in EDC | Category | Severity |
|---------------|-------------|------------------------|------------------|
| R106W | 1 | R106W | Severe |
| R133C | 2 | R133C | Mild |
| T158M | 3 | T158M | Moderate |
| R168X | 4 | R168X | Severe |
| R255X | 5 | R255X | Severe |
| R270X | 6 | R270X | Severe |
| R294X | 7 | R294X | Mild |
| R306C | 8 | R306C | Mild |
| C298G (L100V) | 9 | Other mutations | Mild |
| G317A (R106Q) | 10 | Other mutations | Mild |
| C421G (Y141X) | 11 | Other mutations | Unknown |
| C455G (P152R) | 12 | Other mutations | Severe |
| C302G (P101R) | 13 | Other mutations | Severe |
| C401G (S134C) | 14 | Other mutations | Severe |
| C423G (Y141X) | 15 | Other mutations | Unknown |
| C468G (D156E) | 16 | Other mutations | Mild |
| C674G (P225R) | 17 | Other mutations | Mild |
| C965T (P322L) | 18 | Other mutations | Mild |
| 710del1 | 19 | Other mutations | Severe |
| 806del1 | 20 | Other mutations | Severe |
| 807del1 | 21 | Other mutations | Severe |
| 1157del41 | 22 | C-terminal Truncations | Mild |
| 1157del44 | 23 | C-terminal Truncations | Mild |
| 1163del26 | 24 | C-terminal Truncations | Mild |
| 1163del35 | 25 | C-terminal Truncations | Mild |
| 1164del44 | 26 | C-terminal Truncations | Mild |
| 1168del6 | 27 | C-terminal Truncations | Mild |
| Exon 1+2 | 28 | Large Deletions | Severe |
| Exon 3 | 29 | Large Deletions | Severe |
| Exon 3+4 | 30 | Large Deletions | Severe |
| Exon 4 | 31 | Large Deletions | Severe |
| Exons 1-4 | 32 | Large Deletions | Severe |
| All Others | 33 | Other mutations | Derived from CRF |

Missing and unknown severity will not be imputed.

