13. METHODS OF EFFICACY ANALYSES

13.1 Analysis of Continuous Efficacy Endpoints

Descriptive statistics for all efficacy endpoints listed in [Section 12.1](#) will be tabulated by treatment group of the antecedent study. The summaries of the change from baseline results will be presented in two ways (main analysis and exploratory analysis) as specified in [Section 5.1](#).

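### Efficacy 95% intervals use a fixed 1.96 × SE at every sample size: negligible at the planned visits of the main tables, too narrow wherever a cell is small

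*SAP*

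**What the plan says.** SAP 5.1 gives one rule for interval estimates of efficacy: "For descriptive summaries of efficacy, the 95% confidence interval (CI), calculated as" the mean plus or minus 1.96 standard errors. The exception clause that opens the next sentence concerns decimal places, not this formula. No other section gives a t-based or small-sample rule.

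The rule applies to tables of different sizes:

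- **Main tables.** SAP 12 states "Descriptive summaries of all efficacy endpoints will be presented", and SAP 13.1 says these "will be tabulated by treatment group of the antecedent study". SAP 5.1 adds an overall column. On size, SAP 3.5 says "Up to approximately 180 subjects will be enrolled".
- **Visits listed.** SAP 12.1 lists change in every scale, including both ICND scores and the RTT-CBI total, at Weeks 2, 12, 26 and 40. The schedule (SAP 21.1; Protocol 6.1.4 and 6.1.9) collects the ICND after Baseline only at Week 40/EOT/ET, and the RTT-CBI only at Week 12 and Week 40/EOT/ET. SAP 5.5.1 assigns early-termination and unscheduled assessments to planned visits by study day.
- **Optional subgroups.** Under SAP 12.5, analyses by MECP2 "mutation groupings may be performed for RSBQ and CGI-I".

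SAP 5.1 also puts the number of subjects, SD and SE in each summary. SAP 1 notes: "Specifications for tables, figures, and listings are contained in a separate document".

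**The concern.** The value 1.96 is the two-sided 95% point of the normal distribution. It gives 95% coverage when the standard error is known. Here the SE comes from the same subjects as the mean, so for normal data the correct multiplier is the t quantile on n−1 degrees of freedom, which exceeds 1.96 at every finite n. The gap is trivial in large cells and grows quickly in small ones.

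At stake is the honesty of the label. In a small cell, an interval headed 95% would cover the true mean less often than that, and the estimate would look more precise than it is. A reader comparing a sparse cell with a full one would understate the uncertainty in the sparse one.

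**Working it through.** **Inputs from the documents.** Multiplier 1.96, two-sided 95% (SAP 5.1). Up to about 180 subjects (SAP 3.5). Two prior-treatment groups, one trofinetide and one placebo (Protocol 1.4).

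**Assumed.** An even split by prior treatment, 180/2 = 90. The documents give neither the ratio nor the expected retention.

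**Reproducing the plan's figure.** The 97.5th percentile of the standard normal is 1.95996, which rounds to 1.96. The stated multiplier is therefore the normal quantile.

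**Formulas**, for normal data with F the t distribution function on n−1 degrees of freedom:

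- Coverage = 2 × F(1.96) − 1
- Shortfall in width against the t interval = 1 − 1.96 / t(0.975, n−1)

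For example, at n=8: t(0.975, 7) = 2.365, and 1 − 1.96/2.365 = 17.1%.

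| n | Where it might apply | t quantile | Coverage of mean ± 1.96 SE | Too narrow by |
|---|---|---|---|---|
| 180 | Overall column at entry | 1.973 | 94.8% | 0.7% |
| 90 | One prior-treatment column, even split assumed | 1.987 | 94.7% | 1.4% |
| 45 | Same column if half remained (assumed) | 2.015 | 94.4% | 2.7% |
| 16 | Hypothetical small cell | 2.131 | 93.1% | 8.0% |
| 8 | Hypothetical small cell | 2.365 | 90.9% | 17.1% |
| 5 | Hypothetical small cell | 2.776 | 87.8% | 29.4% |

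**Where small cells could arise.**

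1. *Listed analyses with no planned assessment.* Setting the visits in SAP 12.1 against the schedule leaves five scale-and-visit combinations without planned data, counting the ICND once: ICND at Weeks 2, 12 and 26, and RTT-CBI at Weeks 2 and 26. The windows in SAP Table 2 are contiguous (days 2–49, 50–133, 134–231 and 232–310). An early-termination ICND on day 100, for instance, enters the Week 12 cell. Apart from scheduled visits held far off their date, these cells hold only early-termination or unscheduled values.
2. *Optional MECP2 subgroups of RSBQ and CGI-I.* The 16 and 8 in the table are what an even spread of 180 subjects over the 11 categories in SAP 12.5.1 would give (180/11 = 16.4), and half of that after a split by prior treatment (180/22 = 8.2). They are illustrations; actual counts are not in the documents.

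**Check on a discrete scale.** A simulation of 200,000 samples per n used an assumed CGI-I distribution (probabilities 0.02, 0.13, 0.35, 0.35, 0.10, 0.04 and 0.01 for scores 1 to 7):

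| n | Coverage with 1.96 | Coverage with t |
|---|---|---|
| 90 | 94.6% | 94.9% |
| 16 | 93.0% | 94.9% |
| 8 | 91.1% | 95.1% |
| 5 | 89.9% | 94.8% |
| 3 | 77.5% | 90.8% |

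The t quantile restores about 95% down to n=5 in this example. At n=3 it does not fully do so.

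**The case against.** The strongest reply is that little depends on this. No hypothesis is tested, the formula is stated openly, and n, SD and SE stand beside each mean, so any reader can rebuild the t interval. In the full columns, 1.96 is an ordinary large-sample convention. All of that stands, and it limits the importance of the point. It does not make the multiplier right in a small cell.

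It can also be said that the subgroup case is a chain of conditions. The analysis is optional, it may not show means with intervals, and a CGI-I subgroup could report the response rate, to which a t interval for a mean does not apply. The separate table specifications may settle this. That also stands, and it is why the subgroup figures are only illustrations.

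From that chain a reader might infer that the problem can appear only if the MECP2 subgroups are run. The documents do not support this: the ICND and RTT-CBI cells above belong to analyses that SAP 12.1 lists without any option. Those cells owe their existence to the visit list rather than to the interval formula, but the formula would still be applied to them.

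**Conclusion.** The point holds as a minor one. SAP 5.1 makes every efficacy interval narrower than the t interval. At the planned visits of the main tables the loss is under 1.5% of width with 90 or more subjects, and 2.7% even with 45. In small cells it can be material: about 8%, 17% and 29% of width at 16, 8 and 5 subjects.

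The coverage figures assume normal data and are approximate for a 7-point scale. The column size of 90 assumes an even split, and 45 assumes that half remain. No small-cell count can be taken from the documents.

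Two stronger readings should be resisted. A reader might infer that the principal efficacy intervals overstate precision in a way that matters; the figures for 180 and 90 subjects show otherwise. A reader might also take 16, 8 or 5 as expected cell sizes, or as bounds; the documents support neither. No tested conclusion is affected, because none is planned.

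**What to change.** In SAP 5.1, define the efficacy interval as the mean plus or minus t(0.975, n−1) × SE, where n is the number of subjects contributing to that cell.

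The cost is one phrase in the SAP and the matching line in the programs. Intervals widen by 0.7% at n=180 and 1.4% at n=90 (1.973/1.96 and 1.987/1.96), so the main tables hardly change. Small-cell intervals become visibly wider, by about 21% at n=8 (2.365/1.96) and 42% at n=5 (2.776/1.96), which is the purpose.

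The change has limits. At very small n on a discrete scale such as the CGI-I, the t interval is itself only approximate. It also does not resolve the mismatch between the visits in SAP 12.1 and the schedule for the ICND and RTT-CBI, which needs its own correction.
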